8.4. Secondary Endpoints

The secondary endpoints for this study include the following. For these endpoints, baseline is defined as the last assessment prior to the first dose of study drug.

Efficacy Endpoints:

- Subject-rated pain due to acute back spasm using an NRS (0-10 scale, from no pain to worst possible pain) on Day 4 “right now”.
- Subject rating of medication helpfulness (SRMH; 1-5 scale, from poor to excellent) on Days 4 and 14.
- Subject-rated NRS (0-10 scale) of pain due to acute back spasm on Days 1 to 14; average over the past 12 hours.
- Subject-rated NRS (0-10 scale) of pain due to acute back spasm on Days 1 to 14; average over the past hour.
- Subject-rated NRS (0-10 scale) of average pain due to acute back spasm on rest or movement, rated at the end of the day on Days 1 to 14.
- Time to relief of pain from baseline due to acute back spasm using subject-rated NRS (0-10 scale) on Days 1 to 14.

- Clinician’s Global Impression of Severity (CGI-S) (1–5 scale) at baseline (Day 1).
- Clinician’s Global Impression of Change (CGI-C) 1-7 scale from worse to marked improvement) on Days 4 and 14.
- Patient’s Global Impression of Severity (PGI-S) (1-5 scale) at baseline (Day 1).
- Patient’s Global Impression of Change (PGI-C) based on subject’s global assessment (1-7 scale, from worse to marked improvement) on Days 4 and 14.
- Functionality assessment: fingers to floor distance (FFD) is an index of mobility of the spinal cord and is measured as distance in cm when standing with the spinal cord flexed with complete extension of knee joint, on Days 4 and 14 compared to baseline (Day 1) (assessments should be conducted at the same time of day for all three time points).
- Disability assessment at baseline (Day 1), Day 4, and Day 14:
 - Oswestry Pain and Disability (ODI) questionnaire (10 questions with one answer each for pain intensity, personal care, lifting, walking, sitting, standing, sleeping, sex life [if applicable], social life, and traveling).
- Use of rescue medications (measured daily, assessed as number of rescue tablets administered by the subject via smartphone/use of trial application). Patients are instructed not to take rescue medications on the day of clinic visits on Day 4 and 14.
- Quality of sleep rated by subjects starting at baseline (Day 1) and on Days 2 to 14.
- Visual Analogue Scale (VAS) score for subject-reported sleepiness measured in the clinic on at Day 4.

Safety Endpoints

- Clinical evaluations include:

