9.1. Inclusion Criteria

1. Ambulatory male or female, 18 to 65 years of age.
2. Current acute back pain and/or stiffness due to acute and painful muscle spasm starting within 7 days prior to study entry and more than 8 weeks after the last episode of acute back pain.
3. Subjects must have pain of 4 or more on the subject “right now” rating of pain intensity NRS scale of 0 – 10 points at baseline.
4. Must be willing to discontinue all medication used for the treatment of pain or muscle spasm on study entry at Day 1 including but not restricted to:
 - a. Ibuprofen (Motrin)
 - b. Diclofenac (Voltaren)
 - c. Celocoxib (Celebrex)
 - d. Naproxen (Aleve)
 - e. Tolmetin (Tolectin)
 - f. Cyclobenzaprine (Flexeril)
 - g. Cyclobenzaprine (Amrix)
 - h. Metaxolone (Skelaxin)
 - i. Methocarbamol (Robaxin)
 - j. Other nonsteroidal anti-inflammatory drugs (NSAIDs; e.g., aspirin)
 - k. Carisoprodol (Soma)
 - l. Tizanidine (Zanaflex, Sirdalud)
5. Pain localized below the neck and above the inferior gluteal folds.
6. Body mass index ranging between 18 and 35 kg/m².
7. All subjects must be capable of understanding and complying with the protocol and have signed the informed consent document.
8. Female subjects must have a negative urine pregnancy test at screening, must be postmenopausal (amenorrhea for at least 2 years), surgically sterile, or practicing or agree to practice an effective method of birth control if they are sexually active before study entry, during the study and for 2 weeks after the end of the study by using an acceptable method of contraception. Acceptable methods of birth control must be used for at least 14 days prior to the use of study drug. Acceptable methods of birth control include oral, injectable, subdermal implant, vaginal or patch contraceptives, intrauterine device (IUD; copper or hormonal IUD), or double-barrier method (e.g., condom, diaphragm or cervical cap with spermicidal foam, cream, gel, or suppository).
9. Subjects must be willing and able to comply with scheduled visits, treatment plan, laboratory tests, and other study procedures.

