12.8. Use of Rescue Medications

Concomitant use of rescue analgesia used during the study will be recorded as concomitant medications on the eCRF (see [Section 14](#) for allowed and disallowed medications during the study) and will be analyzed at the time of report following dosing of study drug through Visit 4 (Day 28). Subjects will receive acetaminophen (500 mg tablets) (Tylenol) for use as rescue medication if needed for pain during the study. Use of rescue medication will be recorded daily via smartphone/use of trial application . Subjects are instructed to not take any rescue medications on the day of the clinic visits, Days 4 (Visit 2) and 14 (Visit 3).

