Use of rescue medications will be summarized using frequency counts and percentages by generic drug name. Average daily use and total use will be tabulated using descriptive statistics. The Shapiro-Wilk test will be used to examine the assumption of normality. If this test is statistically significant (i.e., $p \leq 0.05$) then the assumption of normality is violated and the total rescue medication consumption will be analyzed using a Wilcoxon Rank Sum test. Results will be expressed as median (range) and p-values. However, if the assumption of normality holds (i.e., Shapiro-Wilk p-value > 0.05), then the total rescue medication consumption will be analyzed using an analysis of variance (ANOVA) model with randomized treatment as the main effect. Results will be expressed as means, SDs, and least squares mean difference (LSMD) and SEs with associated 95% CI, and p-values.

All other secondary endpoints will be summarized by dose using descriptive statistics. In addition, the comparison of each group to placebo will be conducted using an ANCOVA model, adjusting for baseline.

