5.2 Secondary Study Objective

The secondary objectives of this study are to:

- Assess the safety and tolerability of tolperisone in subjects with pain due to acute back spasm;
- Determine the onset of action of tolperisone in treatment of pain due to acute back spasm;
- Determine the duration of pain relief of tolperisone in treatment of pain due to acute back spasm; and
- Determine the need for rescue medication when treated with various doses of tolperisone for pain due to acute back spasm.

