6.4.2.4.4 Prior and Concomitant Medications

Concomitant use of medications, including rescue analgesia other than study-provided acetaminophen taken for acute back spasms, used during the study will be recorded as concomitant medications on the eCRF (see Section 13 of the study protocol for allowed and disallowed medications during the study) and will be analyzed at the time of report following dosing of study drug through Visit 4 (Day 28).

6.4.3 *Population Pharmacokinetics (PK)*

Blood samples for the determination of plasma tolperisone concentrations will be drawn on Day 4 (Visit 2) after completion of all study assessments for a subset of subjects.

6.5 **Data Quality Assurance**

Report summaries will be generated using validated Base SAS[®] software, version 9.4 or higher, on a PC or server-based platform. Additional validated software may be used to generate analyses, as needed.

All SAS programs that create outputs or supporting analysis datasets will be validated by a second statistical programmer or biostatistician. At a minimum, validation of programs will consist of a review of the program log, review of output or dataset format and structure, and independent confirmatory programming to verify output results or dataset content. Additionally, all outputs will undergo a review by a senior level team member before finalization.

The content of the source data will be reviewed on an ongoing basis by project statistical programmers and statisticians. Data will be checked for missing values, invalid records, and extreme outliers through defensive programming applications, analysis-based edit checks, and other programmatic testing procedures. All findings will be forwarded to the project data manager for appropriate action and resolution.

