The number of subjects with relief and those censored will be summarized by treatment group for the ITT population. Estimates of the median times will be presented along with their associated 95% confidence intervals. Treatment group comparisons will be summarized with hazard ratios and their associated 95% CI from a Cox Proportional Hazards regression model with treatment as the main effect and p-values from a generalized Wilcoxon test.

The Kaplan Meier plots of time to pain relief by treatment group will be presented and display the subjects with relief and those censored at each study day.

A by subject listing of derived time to relief estimates will also be presented.

7.4.5.9 *Rescue Medication Use*

The use of study provisioned medication will be summarized using frequency counts and percentages for the number of tablets consumed by treatment group for the ITT population. Descriptive statistics will also be presented by treatment group. The number of days of medication use, average daily use (caplets/day of medication use) and total use will be tabulated using descriptive statistics. The frequency and percentage of subjects with rescue medication entry will be presented.

The Shapiro-Wilk test will be used to examine the assumption of normality for total rescue medication use across all dose groups. If this test is statistically significant (i.e., $p \leq 0.05$) then the assumption of normality is violated and the total rescue medication consumption will be analyzed using a Wilcoxon Rank Sum test.

However, if the assumption of normality holds (i.e., Shapiro-Wilk p-value > 0.05), then the total rescue medication consumption will be analyzed using an analysis of variance (ANOVA) model with randomized treatment as the main effect. The LSM and LSMD will be presented with associated 95% CI and p-values comparing each treatment group to placebo.

A data listing of rescue medication use will be presented and include the average number of tablets consumed and total number of tablets rescue medication consumed for each subject.

7.4.5.10 *Oswestry Disability Index*

ODI score (%) will be calculated as $(\text{total score} \times 2) / (\text{number of sections answered} / 10)$, rounded to the nearest integer, where the total score is the sum of the individual section scores.

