medication administered on or after the date of the first dose of study drug through 24 hours after the date of last dose of study drug. If medication time is not available, any medication administered on or after the date of first dose through the day after the date of last dose (+1 day) will be considered concomitant. An after-treatment medication is defined as any medication administered greater than 24 hours (or >1 day) after the date of the last dose of study drug through the date of the follow-up visit (Visit 4/Day 28).

A medication may be defined as both prior and concomitant. If it cannot be determined whether a medication was received prior to the start of study drug dosing due to partial or missing medication start and/or end dates, it will be considered a prior medication. Likewise, if it cannot be determined whether a medication was received after the start of study drug dosing, it will be considered concomitant.

For both concomitant, and after-treatment medications summaries, the number and percentage of subjects receiving any medication will be summarized by treatment group and for total tolperisone treated subjects, as will the number and percentage receiving any medication by ATC drug class and generic drug name.

Subjects reporting use of more than one medication at each level of summarization (any medication received, ATC class, and generic drug name) will be counted only once. ATC class terms will be displayed by descending order of incidence, as will generic drug names within each ATC class. The study phase during which each medication was received (e.g., prior, concomitant, or both) will be presented on the listing of prior and concomitant medications.

A summary of concomitant analgesic medications received, outside of the study-provided medication, will also be presented. These medications will be identified from list of generic drug names and indications as determined by the sponsor prior to data base closure. Analgesic medications taken on Day 1 will not be considered as concomitant as use was allowed per protocol on Day 1 of treatment.

All medications will be presented in a data listing by subject and medication name. The study phase during which each medication was received (e.g., prior, concomitant, or after-treatment) and whether the medication is a rescue medication will be presented on the listing.

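### The only between-group test of rescue use counts study-provided acetaminophen, so a subject who turns to another analgesic instead scores as needing little or no rescue

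*SAP*

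**What the plan says.** The objective is general. SAP 5.2: "Determine the need for rescue medication when treated with various doses of tolperisone for pain due to acute back spasm".

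The protocol endpoint (8.4) is a tablet count: "Use of rescue medications (measured daily, assessed as number of rescue tablets administered by the subject via smartphone/use of trial application". Two other protocol sections look wider. Section 12.8 states: "Concomitant use of rescue analgesia used during the study will be recorded as concomitant medications on the eCRF". Section 17.4.2.2 states: "Use of rescue medications will be summarized using frequency counts and percentages by generic drug name".

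SAP 6.4.1.2 defines the endpoint as tablets of the study-provided acetaminophen 500 mg. SAP 7.4.5.9 follows: "The use of study provisioned medication will be summarized using frequency counts and percentages for the number of tablets consumed by treatment group". Total consumption is compared with placebo by a Wilcoxon rank sum test, or by ANOVA if a Shapiro-Wilk test does not reject normality.

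The SAP knows of other rescue. Section 6.4.2.4.4 describes the concomitant medications on the eCRF as "including rescue analgesia other than study-provided acetaminophen taken for acute back spasms". Section 7.5.5.5 plans a summary of analgesics other than the study-provided one, drawn from a list that the sponsor settles before the database closes. It plans no comparison with placebo. The same section adds: "Analgesic medications taken on Day 1 will not be considered as concomitant as use was allowed per protocol on Day 1 of treatment".

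Protocol inclusion criterion 4 reads: "Must be willing to discontinue all medication used for the treatment of pain or muscle spasm on study entry at Day 1".

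**The concern.** Taking a different painkiller can be a sign that pain is not controlled. In the tested variable, a subject who does so instead of taking study caplets is recorded with few caplets or none, and zero is the best possible rank. If this happens more often in one arm than another, the comparison is distorted. If it is commoner on placebo, a true benefit shrinks. If need is truly equal, active treatment can appear to need more rescue.

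No named sensitivity analysis covers this. Rescue use is in neither the LOCF list (SAP 7.4.6.2) nor the per-protocol list (SAP 7.4.6.6). Excluding subjects for prohibited medication therefore does not, as written, reach the rescue comparison.

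The Day 1 sentence raises a second issue. It takes post-dose analgesics out of the one table meant to show non-study analgesia, on a ground that cannot be found in the protocol.

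**Working it through.** **Texts side by side**

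1. Tested variable: total study-provided acetaminophen, ITT population (SAP 7.4.5.9).
2. Other rescue analgesia: acknowledged (SAP 6.4.2.4.4), summarised without a test (SAP 7.5.5.5).
3. Rescue summary by drug: planned in Protocol 17.4.2.2, absent from SAP 7.4.5.9, and not declared in SAP 7.7.1, although SAP section 4 says changes from the protocol will be explained.
4. Day 1: SAP 7.5.5.5 defines a concomitant medication as one given on or after the date of first dose. Under SAP 7.1.5, that date is Day 1. The Day 1 analgesic sentence departs from this definition and makes no split at the time of first dose, although Protocol 10.1 has dosing start with the midday or evening dose.
5. The permission that the Day 1 sentence relies on: the protocol contains no such statement. Criterion 4 asks for willingness to discontinue on study entry at Day 1.

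**Size**

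The documents give no expected rescue use, SD, power or switching rate for this endpoint, so there is no plan figure to reproduce. What follows is illustration on assumed inputs.

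Assume mean needs of 10 caplets (placebo) and 7 (active), with switchers recorded as zero. Observed difference = 10(1 − s_placebo) − 7(1 − s_active), against a true difference of 3.

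| Switching, placebo / active | Observed difference | Change from 3 |
|---|---|---|
| 5% / 2% | 9.50 − 6.86 = 2.64 | −12% |
| 10% / 10% | 9.00 − 6.30 = 2.70 | −10% |
| 10% / 5% | 9.00 − 6.65 = 2.35 | −22% |
| 20% / 5% | 8.00 − 6.65 = 1.35 | −55% |
| 5% / 10% | 9.50 − 6.30 = 3.20 | +7% |

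The last row shows that the direction depends on who switches.

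Zeros weigh heavily in a rank test, so a simulation was also run: 80 per arm, negative-binomial counts with dispersion 1, 3,000 trials per row, Wilcoxon test at two-sided 5%, random switchers set to zero. Counts were capped at 36, the most allowed by Protocol 7.3.2 (3 a day on 14 − 2 = 12 days). Means are before capping.

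| Switching, placebo / active | Rejection rate, need 12 v 7 | Rejection rate, need 12 v 12 |
|---|---|---|
| none | 79% | 5% |
| 10% / 10% | 64% | 4% |
| 10% / 5% | 48% | 8% |
| 20% / 5% | 10% | 34% |

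In the last two rows with equal need, the mean differences (placebo minus active) are −0.56 and −1.70 caplets: active appears to need more.

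**The case against.** **The SAP follows the protocol endpoint.** This stands. The protocol also counts tablets entered in the app and supplies acetaminophen as the rescue drug. A reader might infer that the SAP narrowed the tested endpoint without saying so. It did not. What it left undeclared is the loss of the descriptive rescue summary by drug from the rescue section. Concomitant medications are still tabulated by generic name in SAP 7.5.5.5. The move from ITT to the Safety Population matters little, since both require receipt of study drug.

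**Other analgesics are reported.** This stands in part. They have their own summary, and every medication, including Day 1 use, appears in a by-subject listing with study phase and a rescue flag. It would be wrong to say that Day 1 analgesics are dropped altogether. The sentence might also be read as governing only the analgesic table, leaving the general concomitant table unaffected. But a listing or an untested summary does not correct the tested total.

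**Use earlier on Day 1 fits criterion 4.** This stands. Subjects may present, enter and start dosing on the same day, so criterion 4 does not state the opposite of the SAP sentence. The defect is that no permission is stated and that use before and after the first dose is treated alike.

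**A zero score needs full substitution.** This also stands. Someone who adds another drug to study caplets can still score high, and 50 caplets are supplied. The bias may be small.

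**Diary pain results are partly protected.** Prohibited medication is a deviation category, major deviations lead to exclusion from the per-protocol set, and that set covers the diary NRS endpoints. Time to relief and rescue are not named there. A reader might infer that any Day 1 analgesic contaminates the first rating eligible for relief. The Day 2 rating at 8-10 am looks back 12 hours, so only intake from about 8-10 pm on Day 1 falls inside its window.

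**Conclusion.** The gap is real and is settled by reading the text: the tested rescue measure omits rescue analgesia that the SAP itself recognises, on a stated secondary objective, with no named sensitivity analysis.

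Its size is not known. The 10% to 55% losses and the simulated rejection rates rest on invented means, invented switching rates and complete substitution. They show that modest unequal switching could matter, not that it will. That switching is commoner on placebo is plausible but undocumented, so neither a fixed bias nor a reversal should be claimed.

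The Day 1 sentence is a separate inconsistency. It conflicts with the SAP's definition of concomitant and cites a permission not found in the protocol. Its direct effect is confined to the analgesic summary: study acetaminophen is captured from Day 1, so the tested total is untouched.

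This is an inexpensive improvement to a secondary analysis. The primary endpoint analysis does not depend on it.

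**What to change.** 1. In SAP 7.4.5.9, keep the caplet total. Add a supplementary ITT comparison of each dose with placebo for any rescue (yes/no) and, where the eCRF dates support it, days with any rescue. Count study acetaminophen from the eDiary, or any other analgesic or muscle relaxant taken for pain from the eCRF.
2. Fix the list of qualifying drugs, blinded and before database lock, by extending the sponsor list already planned in SAP 7.5.5.5.
3. Classify Day 1 analgesics as before or after the first dose where times exist. Where times are missing, show the result both with and without them.
4. Reconcile the Day 1 sentence in SAP 7.5.5.5 with the SAP definition of a concomitant medication and with protocol inclusion criterion 4.
5. In SAP 7.7.1, list these changes and the removal of the rescue summary by drug from the rescue section.

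Cost: SAP wording and one derivation, with no new data collection. Two limits should be stated. The common unit becomes days or yes/no instead of tablets. Protocol section 14 assures only start and stop dates for concomitant medication, so as-needed use entered as an interval may overcount days. That is why the yes/no measure comes first and the count of days is conditional.
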